#### Safety and Tolerability Objectives

Assess the incidence of infusion reactions (IRs), anaphylaxis, gout flares, cardiovascular events, and the adverse event (AE)/serious AE profile overall and potentially attributed to the combination of pegloticase and MTX.

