# 9.6.2 Populations for Analysis

The following analysis populations will be defined for this study:

- Intent-to-treat (ITT) population: all subjects who take at least one dose of MTX
- Modified intention-to-treat (mITT) population: all subjects who receive at least 1 dose of pegloticase
- Pharmacokinetic (PK) population: all subjects who receive at least 1 dose of pegloticase and have a post-pegloticase sample evaluable for PK analysis

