#### 9.6.7 Safety Analysis

Treatment-emergent AEs (TEAEs) during the Run-In period are defined as events with an onset date on or after the first dose of MTX through the first pegloticase infusion, or 30 days after the last dose of MTX for subjects who do not receive pegloticase. TEAEs during the Pegloticase + IMM Period are defined as events that occur after the start of the first pegloticase infusion through 30 days after the last dose of pegloticase and/or MTX (whichever is later). TEAEs during the MTX Run-in Period will be summarized with the ITT population, and TEAEs during the Pegloticase + IMM Period will be summarized with both the ITT and mITT populations. TEAEs during any period (MTX Run-in Period or Pegloticase + IMM Period) will be summarized for the mITT population. AEs that occur more than 30 days after the last dose of pegloticase and/or MTX through the 6 month follow-up visit will also be summarized. The number and percentage of subjects experiencing AEs will be summarized by system organ class and preferred term. Summaries by maximum severity and relationship to MTX and pegloticase

Protocol: HZNP-KRY-201

KRYSTEXXA IND: 010122

Version 3.0, Administrative Change 1

will also be provided. SAEs and AEs leading to discontinuation of MTX and pegloticase will be presented by system organ class and preferred term.

Incidence of IRs, gout flares, and other AEs of special interest will be summarized.

Laboratory test results, including urine uric acid:creatinine ratio, will be summarized by study visit and change from baseline. Shift tables for laboratory parameters by Common Terminology Criteria for Adverse Events grade will be presented. Laboratory test results will also be classified relative to the normal reference range (normal, low, or high).

Vital signs, including blood pressure, respiratory rate, temperature, and heart rate, will be summarized by study visit and change from baseline.

Prior and concomitant medications will be summarized and/or included in the data listings.

Data for the MTX Run-in Period and Pegloticase + IMM Period will be summarized separately, where applicable.

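### The ITT table of pegloticase-period TEAEs counts subjects who were never at risk, and no planned table shows any-period TEAEs in everyone who took methotrexate

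*Protocol*

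**What the plan says.** Protocol section 9.6.2 defines two populations that matter here: "Intent-to-treat (ITT) population: all subjects who take at least one dose of MTX" and "Modified intention-to-treat (mITT) population: all subjects who receive at least 1 dose of pegloticase".

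Section 9.6.7 then assigns them to three TEAE summaries:

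- Run-in: "TEAEs during the MTX Run-in Period will be summarized with the ITT population". The window closes at the first infusion, "or 30 days after the last dose of MTX for subjects who do not receive pegloticase".
- Pegloticase + IMM Period: "TEAEs during the Pegloticase + IMM Period will be summarized with both the ITT and mITT populations". The window covers "events that occur after the start of the first pegloticase infusion through 30 days after the last dose of pegloticase and/or MTX", whichever is later.
- Any period: "TEAEs during any period (MTX Run-in Period or Pegloticase + IMM Period) will be summarized for the mITT population".

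The safety objective in the Synopsis is the adverse event "profile overall and potentially attributed to the combination of pegloticase and MTX". The Synopsis lists methotrexate as a test drug beside pegloticase.

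**The concern.** The design produces subjects who are in ITT but not in mITT. Under sections 9.1 and 9.3.4.3, a subject who cannot tolerate methotrexate 15 mg in the run-in is a screen failure, yet has already taken methotrexate. Eligibility is also checked again at Week -2 and Day 1, so some may leave for other reasons.

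Two consequences follow. First, these subjects stand in the denominator of the ITT table for a period they never entered, which lowers every percentage in it. Second, they are absent from the only summary that spans both periods. That absence is not random. Section 9.4.6.3.2.2 makes run-in failures out of subjects with new cytopenia, hepatic or renal abnormality, rash or oral ulceration, persistent gastrointestinal symptoms and similar findings, and several of these are on the list of methotrexate adverse events in section 7.1.3. An overall profile restricted to subjects who got through the run-in is conditional on having tolerated one of the two test drugs.

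With 12 to 16 subjects, one person moves a percentage by about 6 to 8 points (1/16 = 6.25%, 1/12 = 8.3%), so the choice of denominator is visible in the tables.

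**Working it through.** The protocol gives no figure for the TEAE tables, so there is none to reproduce.

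**Inputs**

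- m, the number infused: 12 to 16, the planned size in section 9.6.9. The Schedule of Assessments places enrollment at Day 1, so this is read as infused subjects.
- k, the number who took methotrexate but were never infused: not given in the protocol. Assumed 0 to 4.
- Illustrative event rate among infused subjects: 26%, the Phase 3 infusion-reaction rate in section 7.1.1.

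**1. Pegloticase-period TEAEs**

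Let x infused subjects have the event. No never-infused subject can.

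- mITT percentage = x/m
- ITT percentage = x/(m+k) = (x/m) × m/(m+k)

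The table gives the factor m/(m+k), and what a true 26% reads on ITT:

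| m | k = 0 | k = 1 | k = 2 | k = 3 | k = 4 |
|---|---|---|---|---|---|
| 12 | 1.00 (26.0%) | 0.92 (24.0%) | 0.86 (22.3%) | 0.80 (20.8%) | 0.75 (19.5%) |
| 14 | 1.00 (26.0%) | 0.93 (24.3%) | 0.88 (22.8%) | 0.82 (21.4%) | 0.78 (20.2%) |
| 16 | 1.00 (26.0%) | 0.94 (24.5%) | 0.89 (23.1%) | 0.84 (21.9%) | 0.80 (20.8%) |

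For k of 1 to 4 the factor runs from 0.94 (m = 16, k = 1) to 0.75 (m = 12, k = 4). The direction is fixed: with any k above 0 the ITT figure is lower for every event that occurs.

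**2. Any-period TEAEs**

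Let a of the m infused and b of the k never-infused subjects have the event.

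- mITT percentage = a/m
- ITT percentage = (a+b)/(m+k)

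The ITT figure exceeds the mITT figure only if b/k > a/m. Take m = 14 and k = 2 (assumed):

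- a = 7, b = 2: mITT 7/14 = 50.0%, ITT 9/16 = 56.25%.
- a = 7, b = 0: mITT 50.0%, ITT 7/16 = 43.75%.
- a = 14, b = 2: both 100%.
- a = 14, b = 0: mITT 100%, ITT 14/16 = 87.5%.

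So the direction is not fixed. What is fixed is that the b subjects' events are absent from the mITT table.

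**3. Where the absence would show**

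Take an event tied to methotrexate intolerance, with assumed counts: 1 of 13 infused subjects and all of the run-in failures stop methotrexate for an adverse event.

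- Three run-in failures: mITT 1/13 = 7.7%, ITT 4/16 = 25%.
- One run-in failure: mITT 7.7%, ITT 2/14 = 14.3%.
- None: 7.7% on both.

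**The case against.** The strongest reply is that nothing is hidden. The sentence that creates the ITT pegloticase-period table also creates the mITT one, which has the right at-risk denominator; the ITT table is an extra view. Events in run-in failures are collected to 30 days after the last methotrexate dose and tabulated on ITT in the run-in summary. This stands, and it keeps the point small.

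A reader might infer that the populations are the wrong way round and that both tables understate harm. The protocol does not support that. For the pegloticase period the correct table is already planned. For the any-period table, infused subjects have about 56 weeks of observation (4 of run-in plus 52), and section 9.5.4.8 has gout flares recorded as adverse events. For any TEAE at all, the mITT percentage may well equal or exceed the ITT one.

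It can also be said that only infused subjects received the combination, so mITT suits the part of the objective about the combination. That is fair, but the same objective asks for the overall profile, and for that the treated population starts with the first methotrexate dose.

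Finally, an any-period ITT table would itself dilute infusion-related events, by the same factor as above, and would pool subjects with a few weeks of methotrexate with others on a year of combination therapy. This also stands. It is a reason to keep the mITT table, not a reason to omit the ITT one.

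**Conclusion.** The point holds in a limited form. The ITT version of the pegloticase-period table includes subjects who by definition cannot have an event. Its percentages are 0.94 to 0.75 of the true at-risk figures for 12 to 16 infused and an assumed 1 to 4 never infused, and unchanged if every methotrexate starter is infused. The mITT version is sound.

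The any-period summary omits methotrexate-exposed subjects who left before infusion, so no planned table shows all TEAEs in all treated subjects. Their events are not lost. Understatement in that table is plausible for methotrexate-intolerance terms and not established for adverse events in general.

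The size rests on the assumed number of run-in failures, for which the protocol gives no figure. The 26% serves only as an example: section 9.6.7 also provides a separate incidence summary for infusion reactions, without naming its population. In a small single-arm study without statistical testing (section 9.6.5), this is a minor improvement in presentation.

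**What to change.** In section 9.6.7, and in the table shells:

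- Name mITT as the denominator for Pegloticase + IMM Period TEAEs. Drop the ITT version, or footnote it as including subjects who were not at risk.
- Add an any-period TEAE summary on ITT, that is, on all subjects who took methotrexate, beside the mITT one.
- Keep the any-period mITT table as the one to read for pegloticase-specific events, since the ITT version dilutes them.

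The cost is a change to one or two sentences and one more table, offset if the ITT pegloticase-period table is dropped. No new data, visits or subjects are needed.

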#### 9.6.8 Interim Analyses

No formal interim analysis is planned for this study. Efficacy and safety data may be summarized after all subjects enrolled in the study have completed the Week 14 visit or discontinued, and after all subjects have completed Week 24 or discontinued. Additional summary of the data may be performed periodically throughout the study, and safety data will be summarized regularly for safety monitoring. Final analysis will occur when all subjects have completed the study.

#### 9.6.9 Sample Size and Power Considerations

A sample size of approximately 12-16 subjects is planned for this study. The primary efficacy endpoint, the proportion of subjects achieving and maintaining sUA <6 mg/dL for at least 80% of the time during Month 6 (Weeks 20, 22, and 24) of the Pegloticase + IMM Period, will be demonstrated to be statistically greater than 43.5% (proportion of responders during Month 6 in phase 3 studies), according to an exact test for proportions with a 5% type I error, if at least 10/13 (77%) responders are observed; in that case, the lower bound of a 95% confidence interval for the proportion of responders will be about 46%.

#### 9.7 Changes in the Conduct of the Study

If any modifications in the experimental design, dosages, parameters, subject selection, or any other sections of the protocol are indicated or required, the Investigator will consult with the Sponsor before any such changes are instituted. Modifications will be accomplished through formal amendments to this protocol by the Sponsor and approved from the appropriate IRB.

The Sponsor's Medical Monitor will consider any requests for exceptions to protocol entry criteria on a case-by-case basis. The Investigator or other health professional in attendance must contact the Sponsor as soon as possible. All protocol deviations and the reasons for such

Protocol: HZNP-KRY-201

KRYSTEXXA IND: 010122

Version 3.0, Administrative Change 1

deviations **must** be documented in the eCRF. In the event of a major protocol deviation, the Investigator and Sponsor's Medical Monitor will determine whether the subject should continue to participate in the study.

The Sponsor has a legal responsibility to report fully to regulatory authorities all results of administration of investigational drugs to humans. No investigational procedures other than those described in this protocol will be undertaken on the enrolled subjects without the agreement of the IRB and Sponsor.

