### 9.3 Selection of Study Population

#### 9.3.1 Inclusion Criteria

Eligible subjects must meet all of the following criteria:

1. Willing and able to give informed consent.

KRYSTEXXA IND: 010122 Protocol: HZNP-KRY-201 Version 3.0, Adminstrative Change 1

2. Willing and able to comply with the prescribed treatment protocol and evaluations for the duration of the study.

- 3. Adult men or women  $\geq$ 18 to  $\leq$ 65 years of age.
- 4. Women of childbearing potential (including those with an onset of menopause <2 years prior to screening, non-therapy-induced amenorrhea for <12 months prior to screening, or not surgically sterile [absence of ovaries and/or uterus]) must have negative serum/urine pregnancy tests during the Screening/MTX Run-in Period; subjects must agree to use 2 reliable forms of contraception during the study, one of which is recommended to be hormonal, such as an oral contraceptive. Hormonal contraception must be started ≥1 full cycle prior to Week -4 (start of MTX dosing) and continue for 30 days after the last dose of pegloticase or at least one ovulatory cycle after the last dose of MTX (whichever is the longest duration after the last dose of pegloticase or MTX). Highly effective contraceptive methods (with a failure rate <1% per year), when used consistently and correctly, include implants, injectables, combined oral contraceptives, some intrauterine devices, sexual abstinence, or vasectomized partner.
- 5. Men who are not vasectomized must not impregnate their female partner during the study and for at least 3 months after the last dose of MTX.
- 6. Hyperuricemia at the Screening, Week -4, or Week -2 Visit of the Screening/MTX Run-in Period, as documented by sUA ≥6 mg/dL.
- 7. Uncontrolled gout, defined as meeting the following criteria:
  - sUA ≥6 mg/dL prior to entry into the Pegloticase + IMM Period (any laboratory tests during screening up to and including during the MTX Run-in Period) and at least 1 of the following:
    - inability to maintain sUA <6 mg/dL on other urate-lowering therapy
    - intolerable side effects associated with current urate-lowering therapy
    - functionally limiting tophaceous deposits (including those detected clinically or by DECT imaging)
- 8. Able to tolerate MTX 15 mg for 4 weeks during the Screening/MTX Run-in Period prior to the first dose of pegloticase.

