# 9.3.2 Exclusion Criteria

Subjects will be ineligible for study participation if they meet any of the following criteria:

- 1. Weight >160 kg (352 pounds).
- Any serious acute bacterial infection, unless treated and completely resolved with antibiotics at least 2 weeks prior to the Week -4 Visit of the Screening/MTX Run-in Period.
- 3. Severe chronic or recurrent bacterial infections, such as recurrent pneumonia or chronic bronchiectasis.

Protocol: HZNP-KRY-201

KRYSTEXXA IND: 010122

Version 3.0, Adminstrative Change 1

4. Current immunocompromised condition, including current or chronic treatment with systemic immunosuppressive agents, including prednisone >10 mg/day or equivalent dose of other corticosteroid.

- 5. History of any transplant surgery requiring maintenance immunosuppressive therapy.
- 6. Known history of hepatitis B virus surface antigen positivity or hepatitis B DNA positivity.
- 7. Known history of hepatitis C virus RNA positivity.
- 8. Known history of Human Immunodeficiency Virus (HIV) positivity (tested at Screening Visit).
- 9. Glucose -6-phosphage dehydrogenase (G6PD) deficiency (tested at the Screening Visit).
- 10. Severe chronic renal impairment (glomerular filtration rate <25 mL/min/1.73 m^2) or currently on dialysis.
- 11. Non-compensated congestive heart failure or hospitalization for congestive heart failure within 3 months of the Screening Visit, uncontrolled arrhythmia, treatment for acute coronary syndrome (myocardial infarction or unstable angina), or uncontrolled blood pressure (>160/100 mmHg) at the end of the Screening/MTX Run-in Period.
- 12. Pregnant, planning to become pregnant, breastfeeding, planning to impregnate female partner, or not on an effective form of birth control, as determined by the Investigator.
- 13. Prior treatment with pegloticase (KRYSTEXXA), another recombinant uricase (rasburicase), or concomitant therapy with a polyethylene glycol-conjugated drug.
- 14. Known allergy to pegylated products or history of anaphylactic reaction to a recombinant protein or porcine product.
- 15. Contraindication to MTX treatment or MTX treatment considered inappropriate.
- 16. Known intolerance to MTX.
- 17. Receipt of an investigational drug within 4 weeks or 5 half-lives, whichever is longer, prior to MTX administration at Week -4 or plans to take an investigational drug during the study.

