#### 9.3.4.3 Screen Failures

Subjects who do not meet all of the inclusion criteria or meet any of the exclusion criteria will be considered screen failures. In addition, subjects who are unable to tolerate MTX at an oral dose of 15 mg weekly during the MTX Run-in Period will be considered screen failures. Screen failure subjects who are females of childbearing potential who took at least one dose of MTX, will receive a Safety Follow-up Phone call/E-mail/Site Visit approximately 30 days after the last dose of MTX to verify at least one ovulatory cycle after the last dose of MTX. If the subject has not ovulated, a urine pregnancy test will be performed at the study site. Screen failure subjects who receive at least 1 dose of MTX and are non-vasectomized males will receive a Phone/E-mail/Site Visit 3 months after MTX discontinuation regarding partner pregnancy.

Screen failure subjects may be allowed to rescreen for the study if both the Investigator and Sponsor are in agreement regarding rescreening and if the Investigator determines that the subject can satisfy all of the eligibility criteria.

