# 9.4.7 Method of Assigning Subjects to Treatment Groups

This study is an open-label, single-arm design in which all subjects will receive the same study drugs (i.e., MTX and pegloticase).

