### 9.5.6 Study Procedures

Subjects who provide informed consent and who meet all the entry criteria for participation in this study will be enrolled.

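### Section 9.7 opens a case-by-case route to exceptions from any entry criterion, which contradicts the protocol's absolute eligibility rules and its own amendment rule

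*Protocol*

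**What the plan says.** The eligibility sections allow no exception. Section 9.3.1: "Eligible subjects must meet all of the following criteria". Section 9.3.2: "Subjects will be ineligible for study participation if they meet any of the following criteria". Section 9.3.4.3: "Subjects who do not meet all of the inclusion criteria or meet any of the exclusion criteria will be considered screen failures". The same section allows rescreening only where the investigator judges that all criteria can be satisfied. Section 9.5.6 enrols those who consent and "who meet all the entry criteria for participation in this study will be enrolled".

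Section 9.7 deals with changes in conduct. Its first paragraph names subject selection among the things that may need modification, and states: "Modifications will be accomplished through formal amendments to this protocol by the Sponsor and approved from the appropriate IRB". Its second paragraph opens: "The Sponsor's Medical Monitor will consider any requests for exceptions to protocol entry criteria on a case-by-case basis". It goes on to require that all deviations and their reasons be recorded in the eCRF, and that the investigator and the Medical Monitor decide whether a subject with a major deviation continues.

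On design, Section 9.4.7 states: "This study is an open-label, single-arm design in which all subjects will receive the same study drugs". Section 9.6.9 states: "A sample size of approximately 12-16 subjects is planned for this study". It sets the response rate against 43.5% from the phase 3 studies. Section 9.6.2 defines three populations: ITT (any MTX dose), mITT (any pegloticase dose) and PK. None depends on eligibility.

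**The concern.** A site reading Section 9.3 learns that failing one criterion ends the matter. A site reading Section 9.7 learns that it may ask the sponsor for an exception. The sentence covers any request and any criterion. On its face it therefore reaches the safety exclusions (for example G6PD deficiency, pregnancy, known allergy to pegylated products, contraindication to MTX). It also reaches the criteria that define the population (sUA of at least 6 mg/dL, uncontrolled gout, tolerance of MTX 15 mg in the run-in).

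Two things are at stake. The first is protection: an exempted subject would carry the risk that an exclusion was written to avoid, with no stated ethics review of that decision. The second is interpretation. With no concurrent control, the response rate has meaning only for a population fixed in advance. Section 9.5.5 calls that population well defined, and the reading against 43.5% leans on this.

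**Working it through.** **1. The provisions side by side**

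| Place | Rule | Room for an exception? |
|---|---|---|
| 9.3.1 | All inclusion criteria must be met | None |
| 9.3.2 | Any one exclusion makes the subject ineligible | None |
| 9.3.4.3 | Failing any criterion means screen failure | None; rescreening needs all criteria satisfied |
| 9.5.6 | Those meeting all entry criteria are enrolled | None |
| 9.7, first paragraph | Changes to subject selection by IRB-approved amendment | Only through an amendment |
| 9.7, second paragraph | Requests for exceptions considered individually by the Medical Monitor | Yes, for any criterion, with no IRB step stated |

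The last row conflicts with each of the others.

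**2. What happens to an exempted subject.** Under Section 9.6.2, one pegloticase infusion places the subject in mITT, one of the two populations used for efficacy in Section 9.6.5. The eCRF record and the deviation review come after the exception has been made. They document it and do not prevent it.

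**3. The protocol's own figure.** Inputs from Section 9.6.9: reference rate 43.5%, 10 responders of 13, 5% type I error (sidedness not stated), lower 95% bound of about 46%. The interval method, Clopper-Pearson, is in Section 9.6.5.1.

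- Lower bound = 0.025 quantile of Beta(x, n − x + 1). For x = 10, n = 13, that is Beta(10, 4): 46.2%. The stated figure is reproduced.
- Exact upper tail = Σ C(13, k) · 0.435^k · 0.565^(13−k) for k from x to 13. For x = 10 it is 0.0155; for x = 9 it is 0.056. Ten is therefore the smallest count at n = 13 that passes at 5%.

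**4. Weight of one subject.** 1/n gives 1/12 = 8.3 points, 1/13 = 7.7 points and 1/16 = 6.25, or about 6.3 points.

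**5. What one subject does near the protocol's mark** (illustration, starting from 10/13)

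| Change | Result | Exact 95% lower bound | One-sided exact p against 43.5% |
|---|---|---|---|
| None | 10/13 = 76.9% | 46.2% | 0.0155 |
| One outcome switched, n fixed | 9/13 = 69.2% | 38.6% | 0.056 |
| An exempted responder removed | 9/12 = 75.0% | 42.8% | 0.028 |
| An exempted non-responder removed | 10/12 = 83.3% | 51.6% | 0.006 |

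The last two rows answer the question that an exception raises, namely the result without that subject. Removing a responder takes the lower bound just below 43.5%, while the one-sided tail stays under 5%. Removing a non-responder moves the result the other way.

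**The case against.** The strongest case against the point has four parts.

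*Considering is not granting.* The sentence authorises no particular waiver. That is true of the wording. But a route for requests has a purpose only if some can be granted, and Sections 9.3 and 9.5.6 leave no room for any.

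*Other text already governs.* The amendment rule in 9.7 can be read as controlling, eligibility is rechecked from Screening through Day 1, and Section 10 requires source records that verify the entry criteria. These are real safeguards, and nothing shows that a waiver of a safety exclusion is contemplated. Still, the protocol does not say which paragraph of 9.7 prevails, and the rechecks do not say what happens once an exception is agreed.

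*The arithmetic measures small n.* This stands. Every subject, eligible or not, carries 6.3 to 8.3 points. Moving from 10/13 to 9/13 switches an outcome at fixed n, which is not what an exception does.

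*No decision hangs on 10/13.* This also stands. The primary objective is estimation, and Section 9.6.5 rules out statistical testing. The 10/13 mark is a benchmark in the sample-size rationale.

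A reader might go further and infer that the clause lets the sponsor steer the primary result. The documents do not support that. Exceptions to entry criteria precede the first infusion, when the subject's response is unknown. No criterion is identified as predicting Month 6 response, and no direction of bias can be derived.

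**Conclusion.** The contradiction holds and needs no calculation. The exception sentence in Section 9.7 cannot be reconciled with Sections 9.3.1, 9.3.2, 9.3.4.3 and 9.5.6, or with the amendment rule in the preceding paragraph. As written, it leaves open the enrolment of subjects who meet a safety exclusion or fall outside the defined population, and such subjects count in mITT once infused.

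The effect on the primary endpoint is a sensitivity of 6.3 to 8.3 points per subject across the planned 12-16, and is not a demonstrated bias. The documents do not show that any exception was granted. The illustration in the working assumes one exempted subject among 13 with the result at the protocol's own mark. The point merits correction because the remedy is nearly free and protects both subjects and the meaning of the comparison with 43.5%.

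**What to change.** Reconcile the provisions by deleting the exception sentence from Section 9.7 and putting this in its place:

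- No exceptions to or waivers of the entry criteria are granted.
- The criteria change only through a formal amendment approved by the IRB.
- A subject found after enrolment not to have met a criterion is reported as a major protocol deviation.

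A supportive Month 6 response rate without such subjects would be useful but is optional, and can be left to the SAP. The mITT definition need not change.

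The cost is a short text change at the next amendment. The planned sample size and the 10/13 benchmark are untouched. The downside is that an occasional borderline candidate is lost or must rescreen, for which Section 9.3.4.3 already provides.
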